1 INTRODUCTION – BACKGROUND & RATIONALE

1.1 Disease Background

In the US, 73,000 patients are diagnosed with bladder cancer each year with 80% of tumors classified as non-muscle-invasive bladder cancer (NMIBC). This group of tumors can be restricted to the bladder mucosa (stage Ta or carcinoma in situ [Tis]) or invade the lamina propria (i.e., subepithelial connective tissue; stage T1). They are optimally treated with curative intent by transurethral resection (TUR). However, approximately 30-80% of these patients will present with tumor recurrences or progression to muscle-invasive disease at five years that contribute to the high prevalence of this malignancy ¹. In 2011, there were an estimated 571,000 people with a history of bladder cancer in the United States ². This wide range of risk of recurrence and progression reflects the biologic heterogeneity of these tumors and the limited risk stratification tools available for the practicing urologist. As a consequence, patients diagnosed with NMIBC are committed to long-term surveillance programs that include office visits, cystoscopies and radiological tests making NMIBC one of the most expensive malignancies to manage ^{3,4}. This elevated risk of recurrence provided the impetus to develop adjuvant treatments following tumor resection with the goals to reduce recurrence and progression to muscle-invasive disease. Adjuvant treatments include intravesical instillation of bacillus Calmette-Guérin (BCG) immunotherapy and intravesical chemotherapy.

Despite adequate induction with 6 weekly instillations with BCG followed by maintenance, 38% of patients still developed recurrence, 7% progressed to muscle-invasive disease, 5% presented distant metastatic disease, and 3% died from bladder cancer ⁵. Although serious adverse effects occurs in <5% of patients, BCG frequently causes cystitis, hematuria, malaise, and fever that results in treatment discontinuation in approximately 20% of patients ⁶. The experience with these side effects might also contribute to the dismal adherence of 40% to cystoscopic surveillance among NMIBC survivors ⁷. These results highlight the need to improve the outcomes and treatment of patients diagnosed with NMIBC.

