This phase I study will utilize a 3+3 dose escalation scheme for the study drug pembrolizumab with an initial dose of 1 mg/kg given intravesically to the first cohort of three subjects. Details regarding dose escalation can be found in section 4.3. This study will enroll a maximum of 18 evaluable subjects. Evaluable subjects for toxicity will be those who receive at least one dose of the study drug. Evaluable subjects for response are those who meet the minimum treatment and safety evaluation requirements of the study: i. the subject has received the six doses of BCG and three doses of pembrolizumab planned for the induction phase and has sufficient safety data available to assess the occurrence of dose limiting toxicities; ii. the subject has received at least 1 dose of pembrolizumab out of the total 11 doses planned during the maintenance period.

There is a possibility of adding an expansion cohort of up to 10 subjects to further define safety and efficacy of pembrolizumab. This will be determined by Merck after completion of the dose escalation phase.

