9 STATISTICAL CONSIDERATIONS

This is a Phase I dose escalation study using the 3+3 design with 4 doses. The dose escalation scheme and rules for determining the primary outcome, the maximum tolerated dose, are described in Section 4.3. In order to achieve up to 24 evaluable patients for dose limiting toxicity and MTD determination, up to 27 patients may be accrued to the study. This 3+3 design has a 91% chance (49%, 17%) of dose escalating when the true toxicity rate for that dose is 10% (30%, 50%).

To achieve the secondary objectives, the dose limiting toxicities and adverse events will be presented as descriptive frequencies and proportions. Serious adverse events will be summarized by type, frequency, timing, severity and attribution.

NU Study Number: NU 15U06
Merck Study Number: 3475-265

Exploratory objectives (PK, response, progression, immune markers) will be summarized with descriptive statistics due to the anticipated small study sample size. Progression free survival (PFS) and overall survival (OS) will be analyzed using the Kaplan-Meier method. The median PFS and OS estimates will be reported along with confidence intervals.

Progression free survival (PFS) time is calculated as the time that elapses between the initiation of trial therapy and the day of first documented disease progression or death from any cause (whichever is sooner) for all eligible subjects who receive at least one dose of trial therapy. If subsequent anti-cancer therapy is initiated without a preceding disease progression, PFS will be censored at the time of initiation of the subsequent anti-cancer therapy. If disease progression or death from any cause is not observed prior to completion of study participation or initiation of subsequent anti-cancer therapy, the PFS will be censored as the last available disease assessment.

Overall survival (OS) time is calculated as the time that elapses between the initiation of trial therapy and the date of death from any cause, date of completion of study participation, or date the subject is lost to follow up (whichever is sooner) for all eligible subjects who receive at least one dose of trial therapy. If death from any cause is not observed prior to completing study participation, the OS will be censored as the time of the last available documentation of survival status.

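### The only defined response set is limited to subjects who completed induction and began maintenance; Section 9 should also report response in all treated subjects

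*Combined protocol and SAP*

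**What the plan says.** Section 4.1 defines two kinds of evaluability. For toxicity the bar is low: "Evaluable subjects for toxicity will be those who receive at least one dose of the study drug". For response a subject must meet all of the following:

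- "the subject has received the six doses of BCG and three doses of pembrolizumab planned for the induction phase";
- enough safety data to judge whether a DLT occurred;
- "the subject has received at least 1 dose of pembrolizumab out of the total 11 doses planned during the maintenance period".

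The response objective in Section 2.3.3 is worded for the study population and is assessed at the cystoscopies of weeks 17, 25, 33, 41 and 49. On its analysis Section 9 says: "Exploratory objectives (PK, response, progression, immune markers) will be summarized with descriptive statistics". It gives no denominator, no rule for treated subjects who are not response-evaluable, and no second presentation. In the same section, PFS and OS are defined "for all eligible subjects who receive at least one dose of trial therapy".

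The Section 4.1 paragraph also says "This study will enroll a maximum of 18 evaluable subjects", while Section 9 plans as follows: "In order to achieve up to 24 evaluable patients for dose limiting toxicity and MTD determination".

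**The concern.** Membership of the response set depends on what happens after treatment starts. A treated subject who misses an induction dose, or who never receives maintenance pembrolizumab, drops out of the only response denominator that the plan defines. A reader would take the published figure as the response rate in treated patients. It would be the rate in those who got through induction and into maintenance.

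The exclusion can be linked to toxicity, which is what the trial studies. Section 4.3.1 makes a toxicity delay of more than 2 weeks in pre-induction or induction a DLT. Section 4.4 calls for stopping treatment, after consultation, when toxicity has not settled within 14 days of the scheduled dose. Section 4.11 replaces only subjects who never received the week -2 dose, so a dosed subject who leaves the response set is not made up. What is at stake is the interpretation of an exploratory rate that may inform later trials. The MTD is not at stake.

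**Working it through.** **The plan's own figures.** No exclusion rate, target or precision is stated for response. The only operating characteristic is the 3+3 escalation probability in Section 9, (1−p)³ + 3p(1−p)²(1−p)³. At p = 0.10, 0.30 and 0.50 it gives 0.906, 0.494 and 0.172, which agree with the stated 91%, 49% and 17%. They do not bear on response.

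**Who leaves the set.** The first maintenance dose is due at week 7 and the first scheduled on-treatment cystoscopy is at week 17, 10 weeks later. A subject excluded before week 7 therefore leaves before any scheduled response assessment. Table 5 shows no cystoscopy in follow-up; extra ones are done only if clinically indicated (footnote 4). Response in these subjects is mostly unobserved. An early recurrence found at an unscheduled cystoscopy would be an exception.

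**Formula.** Let f be the share of treated subjects excluded, pc the response rate in the evaluable and pe the rate in the excluded. Then:

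- reported rate − all-treated rate = f × (pc − pe);
- with q = pe/pc, reported rate ÷ all-treated rate = 1 / (1 − f(1 − q)).

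The sign depends on pe and the size on f. The documents give neither for this trial.

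**Illustration (all inputs assumed).** N = 24 comes from Section 9. The nearest figure to an exclusion rate is in Section 1.1, where BCG toxicity "results in treatment discontinuation in approximately 20% of patients". That is a cited historical figure, not tied to induction. 20% × 24 = 4.8, so take 5 excluded and 19 evaluable, with an assumed 8 responders.

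| Quantity | Result |
|---|---|
| Reported rate | 8/19 = 42.1% (Clopper-Pearson 95% CI 20.3% to 66.5%) |
| All treated, none of the 5 respond | 8/24 = 33.3% |
| All treated, all 5 respond | 13/24 = 54.2% |
| Reported minus all-treated | +8.8 to −12.1 points |
| Responders among the 5 that give no bias | 5 × 8/19 = 2.1 |

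With f = 5/24, the ratio of reported to all-treated rate is 1.26, 1.12, 1.00 and 0.95 for q = 0, 0.5, 1 and 1.25.

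With only 2 of 24 excluded and an assumed 11/22 = 50.0%, the all-treated rate lies between 11/24 = 45.8% and 13/24 = 54.2%. In both cases the whole range falls inside the confidence interval of the reported rate (28.2% to 71.8% for 11/22).

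**Counts in the same paragraph.**

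- Evaluable subjects: Section 4.1 says 18. Section 9 says up to 24, which equals the 4 dose levels of Table 4-2 × 6. Three levels × 6 would give 18.
- Maintenance doses: Section 4.1 says 11. The Study Summary, the dose list earlier in Section 4.1 and Table 4-1 give 6 (weeks 7 to 17) + 8 (weeks 21 to 49) = 14. Section 1.3.2 prints weeks 23, 29, 35, 41 and 47 after week 17, and 6 + 5 = 11.

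**The case against.** The strongest reply is that the set is openly pre-defined, response is exploratory and descriptive, and PFS in all eligible treated subjects already captures a closely related event, since Section 2.3.4 defines progression by positive resection or biopsy. Also, because excluded subjects mostly leave before a scheduled cystoscopy, the set largely reflects missing outcomes rather than discarded ones, and an all-treated rate must lean on imputation or unscheduled findings. All of this stands, and it keeps the point minor. It does not supply a response denominator matching the stated objective.

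A reader might infer more than the documents support:

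- **That every early stopper is excluded.** A subject who completes induction, has sufficient DLT data, receives one maintenance dose of pembrolizumab and then stops remains evaluable.
- **That a DLT means exclusion, so toxic dose levels lose more subjects from their response tables.** Section 4.4 lets treatment resume after resolution, and Section 9 specifies no response table by dose level.
- **That reasons for leaving are ignored.** Section 4.10 has reasons for discontinuation documented. What is missing is a commitment to show them beside the response rate.
- **That Section 9 adopts the Section 4.1 set outright.** The link is an inference, though no other response set is defined.
- **That a half-dose BCG instillation counts, or does not count, towards the six.** Section 4.4 permits the reduction but is silent on evaluability.

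**Conclusion.** The point holds as a minor one. On the natural reading, the exploratory response rate describes subjects who completed induction and began maintenance, and the plan gives no all-treated rate to set beside it.

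It is tempting to say that the rate is inflated. The documents do not support that: the bias is upward if excluded subjects respond less often than evaluable ones, nil if equally often, and downward if more often. The 20% discontinuation figure is no forecast either. It is not specific to induction, and Section 3 bars patients who could not complete earlier induction BCG because of toxicity. The 33% to 54% range rests on an assumed 5 of 24 excluded and an assumed 8 responders.

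The mismatches of 18 with 24 and of 11 with 14 are separate contradictions within the protocol. The second cannot alter a rule that needs only one maintenance dose.

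**What to change.** In Section 9:

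- Report response among all eligible subjects with at least one dose, beside the rate in the Section 4.1 set, using any recurrence assessment available from clinical follow-up.
- Count unassessed subjects as non-responders and label that rate a conservative lower bound, not an unbiased estimate.
- Tabulate the number excluded from the Section 4.1 set, with the discontinuation reasons already documented under Section 4.10.
- State that the response summary uses the Section 4.1 set, if that is intended, and whether a reduced BCG dose counts towards the six for evaluability.

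In Section 4.1, reconcile the 18 evaluable subjects with the 24 in Section 9. Reconcile the 11 maintenance doses with the 14 listed elsewhere, together with the schedule printed in Section 1.3.2.

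The cost is wording and one table. The lower bound may sit well below the truth, because follow-up schedules no cystoscopy and withdrawal of consent ends follow-up. The response change leaves the MTD rule, the DLT definition and the sample size as they are.

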4.2 Treatment Administration

Table 4-1: Treatment Summary				
	Agent	Dose *	Route	Schedule
Pre-induction Phase	Pembrolizumab	Variable depending on cohort	Intravesically	Once at week -2 (Day -14)
Induction Phase	BCG	50mg	Intravesically	Once per week, weeks 0-5^
	Pembrolizumab	Variable depending on cohort	Intravesically	Once at weeks 0, 2, 4
Maintenance Phase	BCG	50mg	Intravesically	Weeks 7, 9, 11, 13, 15, 17, 21, 25, 29, 33, 37, 41, 45, 49
	Pembrolizumab	Variable depending on cohort	Intravesically	

* Pembrolizumab dose cohorts: 1 mg/kg, 2 mg/kg, 5mg/kg and 10 mg/kg.

^ Treatments should occur +/- 2 days from the same day each week.

4.2.1 BCG

BCG will be administered weekly during the Induction phase of treatment, followed by maintenance BCG (see duration of therapy; section 4.8). Every effort should be made to administer treatments on the same day each week, however a window of +/- 2 days is allowed to accommodate scheduling issues. BCG administration should begin at least 2 weeks after any prior cystoscopies or intravesical procedures to allow healing of bladder epithelium. Each BCG dose will consist of 50mg BCG (TICE® BCG) diluted in 50ml of sterile normal saline that will be injected into the bladder through sterile urethral catheterization. There will be no dose escalation planned for BCG, however the dose may be reduced based on toxicity criteria in section 4.4. After emptying the bladder, the BCG solution will be injected intravesically over 1 or 2 minutes and retained for 2 hours. Following the administration, patients will receive instructions to drink large amounts of fluids and monitor for symptoms that can develop and be related to the BCG instillation: dysuria, urgency, frequency, hematuria, persistent fever (temperature above 101°F for more than 2 days), chills, night sweats, malaise, arthralgia, cough, or skin rash.

4.2.2 Pembrolizumab

Pembrolizumab treatment will start two weeks prior to BCG administration (week -2). Patients will receive three instillations of pembrolizumab concomitant with BCG (weeks 0, 2, and 4; induction period), followed by maintenance pembrolizumab (see duration of therapy; section 4.7). The dose that subjects receive will depend upon the cohort to which they are enrolled; the starting dose will be 1 mg/kg. Each pembrolizumab dose will be diluted in 50ml of sterile normal saline and injected into the bladder through sterile urethral catheterization during 1 or 2 minutes and retained for 2 hours. During the days that BCG and pembrolizumab are given concomitantly, BCG will be administered and immediately followed by pembrolizumab administration; each medication will be diluted in 50ml and the total volume of 100ml will be retained for 2 hours. If pembrolizumab administration is scheduled on the same day as the cystoscopy (weeks 17,

NU Study Number: NU 15U06
Merck Study Number: 3475-265

25, 33, 41, and 49), pembrolizumab may be injected through the cystoscope provided no abnormal findings were noted.

4.3 Dose Escalation Scheme

There will be no dose escalation for BCG (patients on all cohorts will receive the same dose). The table below summarizes the pembrolizumab dose levels; subjects will receive the same dose of pembrolizumab during pre-induction, induction and maintenance phases. No dose reductions are permitted for pembrolizumab. BCG may be reduced for toxicity as described in section 4.4. A standard “3+3” dose escalation design will be utilized. Initially, the study will enroll 3 subjects at the starting dose (level 1), after which enrollment will be temporarily suspended until all 3 patients complete the DLT evaluation period (defined as the 2 week pre-induction phase and the seven weeks of induction phase). Once all 3 subjects complete the DLT period and toxicity data has been reviewed by the Northwestern University Data Monitoring Committee, a decision will be made to proceed with escalation accordingly the rules below.

Table 4-2: Escalation Dose Levels			
Dose Level	Pembrolizumab	BCG	Number of patients
1	1 mg/kg	50mg	3-6
2	2 mg/kg	50mg	3-6
3	5 mg/kg	50mg	3-6
4	10 mg/kg	50mg	3-6

The following rules will be used at each dose level to determine whether or not to proceed to the next dose level:

- If 0 of 3 subjects at a given dose level experience a DLT (defined below), then escalation will proceed to the next dose level.
- If 2 or 3 of 3 subjects at a given dose level experience a DLT, then one of the following must occur:
 - If this happens at level 1, the study will be closed to further accrual and the regimen of pembrolizumab + BCG will be considered too toxic at any dose.
 - If this happens at level 2 or beyond, the previous level will be declared the maximum tolerated dose (MTD).
- If 1 of 3 subjects at a given dose level experiences a DLT, then an additional 3 slots will be added (for a total of 6 patients at that level):
 - If 1 of 6 total experiences a DLT, then escalation will proceed to the next level.
 - If ≥ 2 of 6 total experience a DLT, the previous level will be declared the MTD.

NOTE: Whichever dose level is declared the MTD must have 6 total subjects treated at that level. For example, if 3 subjects are treated at level 2 and 0 subjects experience DLT, escalation would then proceed to level 3. However, if ≥ 2 subjects at level 3 experience DLT, enrollment to level 2 would need to be re-opened to enroll an additional 3 subjects at that level (with 0 or 1 DLT observed in 6 total subjects) in order to declare level 2 the MTD. If dose level 3 is achieved without MTD-defining DLT, dose level 3 will be considered the recommended phase II dose for future trials.

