1.3.2 Rationale for Dose Selection

In the first in human study (Protocol number 001, refer to IB), which treated a variety of tumor types, pembrolizumab showed evidence of target engagement and objective evidence of tumor size reduction at all dose levels (1 mg/kg, 3 mg/kg and 10 mg/kg every 2 weeks). No DLT was observed and no MTD reached at these dose levels. Dose level 10 mg/kg every 3 weeks was evaluated in previously treated patients with NSCLC in Part C of Protocol 001. Pembrolizumab has also shown signs of efficacy and acceptable PK and PD results when administered both every 2 weeks and every 3 weeks. PK data analysis of pembrolizumab administered intravenously every 2 weeks showed slow systemic clearance, limited volume of distribution, and a long half-life (refer to IB).

Pharmacodynamic data (IL-2 release assay) suggested that peripheral target engagement is durable (>21 days). Previously treated patients with NSCLC in PN001 Part C have experienced durable objective responses with acceptable toxicity when treated with pembrolizumab at 10 mg/kg every 3 weeks. Preliminary data in patients with melanoma and NSCLC demonstrates objective responses by pembrolizumab when administered at the 2 mg/kg every 3 weeks dose and schedule. These results document efficacy results with both 2 mg/kg and 10 mg/kg doses. The additional dose level of 1 mg/kg was selected based on efficacy estimated by PK-PD modeling studies (discussed below) and concerns with safety given multiple intravesical administrations.

A syngeneic mouse tumor efficacy experiment, that included PK sampling and tissue receptor occupancy was conducted with a surrogate antibody and analyzed by translational PK-PD modeling. Results were extrapolated to man with inclusion of human relevant parameters for PK, pembrolizumab binding properties to PD-1 and the FcRN receptor, and

NU Study Number: NU 15U06
Merck Study Number: 3475-265

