2 OBJECTIVES & ENDPOINTS

2.1 Primary Objective & Endpoint

The primary objective of this phase I dose-escalation study will be to determine the maximum tolerated dose (MTD) of the study drug (pembrolizumab) when administered intravesically in combination with BCG in patients with high risk or BCG-refractory non-muscle-invasive bladder cancer (up to the individual maximum tolerated dose of each drug alone). The MTD will be defined as the highest dose that causes dose limiting toxicities (DLTs) in <2 of 6 patients.

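### Section 4.3 has no workable rule for ending escalation when level 4, the top dose level, clears

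*Combined protocol and SAP*

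**What the plan says.** Section 9 describes the design: "This is a Phase I dose escalation study using the 3+3 design with 4 doses". The last row of Table 4-2 is "4 10 mg/kg 50mg 3-6", so level 4 may hold three to six subjects and nothing lies above it.

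Section 4.3 gives two clearing rules for each level: "If 0 of 3 subjects at a given dose level experience a DLT (defined below), then escalation will proceed to the next dose level", and, after expansion, "If 1 of 6 total experiences a DLT, then escalation will proceed to the next level". Two or more DLTs at level 2 or above make the level below the MTD. Three further slots are opened after 1 of 3. The NOTE that follows adds "Whichever dose level is declared the MTD must have 6 total subjects treated at that level", and its example re-opens a lower level when the one above fails. The NOTE ends by making level 3 the recommended phase II dose if that level is achieved without MTD-defining toxicity. It gives no number of subjects for that.

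Section 2.1 defines the primary endpoint: "The MTD will be defined as the highest dose that causes dose limiting toxicities (DLTs) in <2 of 6 patients".

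**The concern.** The rules work at levels 1 to 3, and they work at level 4 if it fails. They break down if level 4 clears. Both clearing outcomes send the team to a level that does not exist, no rule declares an MTD, and the only closing sentence points to level 3. That sentence fits the three-level scheme in place before Amendment 1 added 5 mg/kg as a fourth level.

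The primary endpoint therefore has no defined result on one branch of the design, and that branch becomes the likely one if toxicity is low. Section 1.3.2 says of the first-in-human study, which went up to 10 mg/kg: "No DLT was observed and no MTD reached at these dose levels". Section 4.5.1 expects limited systemic absorption after intravesical dosing. The team would then have to decide, after seeing the data, how many subjects level 4 needs and what to call the result.

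**Working it through.** **Inputs.** Four levels and three to six subjects per level (Table 4-2); the clearing and failure rules (Section 4.3); six subjects and fewer than two DLTs for an MTD (Sections 2.1 and 4.3); stated escalation probabilities of 91%, 49% and 17% at true DLT rates of 10%, 30% and 50% (Section 9).

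**Step 1: each possible ending at level 4 against the text.**

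| Result at level 4 | Section 4.3 rules | Section 4.3 NOTE | Section 2.1 |
|---|---|---|---|
| 0 of 3 | go to next level (none exists); no slots added | six needed only for a declared MTD; closing sentence names level 3 | cannot be applied, needs six |
| 1 of 6 | go to next level (none exists) | closing sentence names level 3 | level 4 meets the MTD definition, with no dose-limiting level found |
| 2 or more DLTs | level 3 is the MTD | level 3 must have six subjects | consistent if level 3 has fewer than 2 of 6 |

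Only the last row is settled.

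**Step 2: reproduce the plan's figures.** With true DLT rate p, a level clears with probability E(p) = (1−p)³ + 3p(1−p)² × (1−p)³.

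- p = 0.10: 0.7290 + 0.1771 = 0.906
- p = 0.30: 0.3430 + 0.1513 = 0.494
- p = 0.50: 0.1250 + 0.0469 = 0.172

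These match 91%, 49% and 17%.

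**Step 3: how often the trial sees 0 of 3 at level 4.** Assume the same p at every level. This is not in the documents, so a range is shown. The probability is E(p)³ × (1−p)³.

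| p | reach level 4, E³ | 0 of 3 there, (1−p)³ | product |
|---|---|---|---|
| 0.05 | 0.922 | 0.857 | 79% |
| 0.10 | 0.744 | 0.729 | 54% |
| 0.20 | 0.356 | 0.512 | 18% |
| 0.30 | 0.121 | 0.343 | 4% |

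**Step 4: what three subjects show.** The exact one-sided 95% upper limit for the DLT rate after no events in n subjects is 1 − 0.05^(1/n). For n = 3 it is 63%; for n = 6 it is 39%.

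**Step 5: effect of six subjects at level 4, given that level 4 is reached.** P(0 or 1 of 6) = (1−p)⁶ + 6p(1−p)⁵.

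| p | escalation rule | 0 or 1 of 6 | difference |
|---|---|---|---|
| 0.10 | 91% | 89% | 2 points |
| 0.30 | 49% | 42% | 7 points |
| 0.50 | 17% | 11% | 6 points |

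Check: the difference should equal P(0 of 3) times the chance of at least two DLTs in the next three. At p = 0.30 this is 0.343 × 0.216 = 0.074, as found.

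**The case against.** The strongest reply is that this is only the level 3 wording left over in the NOTE: bring that sentence into line with Table 4-2 and a rule for clearing the top level exists. That would remove part of the gap. It would not say how many subjects the recommended dose needs, since the sentence states none and the six-subject condition is tied to a declared MTD. Nor would it resolve Section 2.1, under which level 4 with 1 of 6 is the MTD.

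A reader might also infer that the protocol lets level 4 be called the MTD on 0 of 3. It does not: Sections 2.1 and 4.3 both require six subjects. Nor does any sentence endorse level 4 as a recommended dose.

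The low-toxicity case is fairly disputed. Experience with the drug given intravenously does not cover this trial's DLTs, which include bladder events, toxicity delays over two weeks, and Grade 2 events lasting more than 10 days. Section 7.2.8 reports bladder irritability in about 60% of patients receiving BCG. This is why a range is given; at 30% the gap is seldom reached. At that rate the six-subject criterion changes the whole-trial chance of clearing level 4 only from 6.0% (0.1207 × 0.4943) to 5.1% (0.1207 × 0.4202). Toxicity rising with dose could make the change larger; that is not modelled here.

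Section 2.1 caps the objective at each drug's own maximum tolerated dose. That does not supply an ending, because Section 1.3.2 reports that no MTD was reached at the doses studied. The expansion cohort of up to 10 subjects (Sections 1.3.2 and 4.1) could add safety data, but it is optional and decided after escalation.

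**Conclusion.** The point holds as an incomplete decision rule for the primary endpoint. After 0 of 3 or 1 of 6 at level 4, Section 4.3 gives an instruction that cannot be carried out, declares no MTD, and points to level 3. After 0 of 3, no rule enrols the three subjects that an MTD would need, and nothing says whether the six-subject criterion covers a recommended dose when no MTD-defining toxicity is seen.

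The size depends on an assumed DLT rate common to all levels: 79%, 54%, 18% and 4% of trials would reach level 4 and see 0 of 3 there at rates of 5%, 10%, 20% and 30%. It would be tempting to cite the 67% of trials that clear all four levels at a 10% rate (0.906⁴), but that includes endings at 1 of 6, which already have six subjects. The differences in Step 5 are conditional on reaching level 4.

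**What to change.** Reconcile Section 2.1, the Section 4.3 rules and NOTE, and Table 4-2, so that Section 4.3 states:

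- what follows 0 of 3 and 1 of 6 at level 4;
- whether the protocol's own six-subject criterion applies to the top level, or to a recommended dose when no MTD is reached;
- how a result without a dose-limiting level is reported: as an MTD, or as the highest dose tested with MTD not reached.

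Reconcile the evaluable totals at the same time: Section 4.1 caps them at 18 (3 × 6), while Section 9 allows 24 (4 × 6).

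The text change is short. If the six-subject criterion is applied at level 4, it adds up to three subjects. These always fit within 24; they fit within 18 only if at most one lower level was expanded (3 + 3 + 6 + 6 = 18). At the accrual rate in Section 3 of one patient every 2 to 3 months, three more subjects take roughly 6 to 9 months, plus the nine-week DLT window for the last of them. If the criterion is not applied, the protocol should say so and acknowledge the 63% upper limit after 0 of 3.
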